# 17.5 Notification of AEs of special interest

Adverse events relating to hepatic decompensation (i.e. development of ascites, encephalopathy, variceal bleeding) are of special interest. These events are expected from the natural progression of the underlying condition being treated, but are of particular relevance in patients with compensated or decompensated cirrhosis, due to reports of decompensation in patients with advanced liver disease treated with DAA therapies.

In addition, cardiac arrhythmias in particular severe bradycardia and heart block have been observed with sofosbuvir when used with concomitant medications which lower heart rate (note amiodarone is prohibited).

Therefore the occurrence of the above adverse events, if graded as serious, should be reported according to the procedures detailed in the section 'Notification and reporting for SAE/SUSAR'. AESIs which are not graded as serious are recorded as for other AEs and do not require reporting.

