#### 12.2 Exclusion Criteria

- Any of the above inclusion criteria not met
- Any of the following criteria excludes a subject from enrolling into this study
- Clinically-significant medical or psychiatric illness (other than chronic HCV) in the past, present, or being evaluated, that may interfere with participant treatment, safety, assessment or compliance with the protocol.
- Severe renal impairment with eGFR <30 mL/min/1.73m^2 or requiring dialysis
- Alcohol consumption or illicit drug abuse likely to interfere with participant treatment, safety, assessment or compliance with protocol, as deemed by the investigator
- Previous exposure to sofosbuvir (or other NS5B inhibitor) or NS5A inhibitor
- Severe allergy to study drugs, its metabolites or formulation excipient (see SmPC for details)
- Any investigational medicinal product ≤ 6 weeks prior to treatment start
- Pregnant or nursing female, or males wishing to conceive during the period of study treatment + 30 days after
- Patients who adhered to less than 90% of prescribed sofosbuvir/velpatasvir at screening
- In accordance with the SmPC of sofosbuvir/velpatasvir concomitant use of the following medications are contraindicated:

Anticonvulsants - carbamazepine, phenytoin, phenobarbital, oxcarbazepine

Antimycobacterials - rifampicin, rifabutin, rifapentine

Antiretrovirals - efavirenz

St John's wort

Modafinil

Proton-pump inhibitors should be avoided and if necessary, should be administered 4 hours after at maximum doses equivalent to 20mg omeprazole per day.

Amiodarone should be avoided and if necessary, close monitoring is required

Please consult the SmPC and Section 15.16 and 17 for list of medications to be used with caution or monitoring.

Participants taking these medications must have discontinued prior to starting sofosbuvir/velpatasvir (this is expected to be in line with standard care practice). Definition of child-bearing potential and effective contraception:

Subjects are considered not of child-bearing potential if they are surgically sterile (undergone a hysterectomy, bilateral tubal ligation, or bilateral oophorectomy) or they are postmenopausal (women aged  $\geq$  45 years of age with cessation of previously occurring menses for  $\geq$  12 months) or they have medically-documented ovarian failure.

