#### Obtain history

- previous HCV treatment experience (pegylated interferon/ribavirin; clinical trial; DAA) note participants exposed to SOF (or other NS5B inhibitor) or DCV (or other NS5A inhibitor) are excluded
- document responses and any adverse events or intolerances to previous treatment, if known

Physical examination - full examination of the cardiovascular, respiratory, gastrointestinal systems as minimum. Assessment of whether the subject has active hepatic decompensation. Other systems as deemed appropriate by investigator.

This should be completed by a study doctor.

Record concomitant medications including over the counter and herbal medications

- review drug-drug interactions (see protocol Trial Medication section, sofosbuvir/velpatasvir SmPC and www.hep-druginteractions.org for guidance)
- prohibited concomitant medications must be discontinued at least 21 days before treatment start as per Exclusions section of protocol
- other investigational medicinal products within 6 weeks of treatment start are excluded
- record if known allergy to any of study drugs

Document if participant is pregnant, breastfeeding, or wishing to conceive during the study treatment period + 30 days after

Document contraceptive and breast feeding advice (if applicable) and currently in use or chosen method of protocol specified contraception.

Record baseline laboratory results and dates (within 3 months of treatment start)

- haemoglobin
- platelet count
- urea & electrolytes, creatinine
- eGFR (using Cockcoft-Gault or MDRD formula) NB eGFR <30ml/hr is an exclusion

- total bilirubin
- ALT
- INR or PT (include lab reference PT range), if available
- Albumin

Record the following regarding current treatment

• start date of sofosbuvir/velpatasvir (treatment week 0)

Record the following between treatment start and screening visit

- Any adverse events/ serious adverse events
- Any treatment discontinuation (of Sofosbuvir/velpatasvir)
- Any missed doses of treatment reported note patient must have at least 90% adherence at screening
- Record batch/lot number and expiry of NHS dispensed bottle of sofosbuvir/velpatasvir

Study doctor must assess whether subject fulfils eligibility.

Note: enrolled participants will complete sofosbuvir/velpatasvir dispensed as part of their NHS treatment and are not dispensed additional study drug, unless they are randomised to the extended treatment arm.

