#### 15.17 Prior and Concomitant medication

To avoid drug-drug interactions, the following list of concomitant medications are not permitted, according to product SmPCs. Participants taking these medications must have discontinued prior to starting sofosbuvir/velpatasvir (this is expected to be in line with standard care practice).

In accordance with the SmPC of Epclusa (sofosbuvir/velpatasvir) concomitant use of the following medications are contraindicated:

Anticonvulsants - carbamazepine, phenytoin, phenobarbital, oxcarbazepine Antimycobacterials – rifampicin, rifabutin, rifapentine

Antiretrovirals - efavirenz

St John's wort

Modafinil

Proton-pump inhibitors should be avoided and if necessary, sofosbuvir/velpatasvir should be taken with food and administered 4 hours before proton pump inhibitor, at maximum doses equivalent to 20mg omeprazole per day.

Amiodarone should be avoided and if necessary, close monitoring is required

The following medications should be co-administered with caution:

Digoxin

Amiodarone

Rosuvastatin (do not exceed 10mg), other statins consider dose reduction Antacids (e.g. aluminium hydroxide) – separate administration by 4 hours

H2 antagonists — administer simultaneously or staggered from sofosbuvir/velpatasvir, at a dose not exceeding the equivalent of 40mg famotidine twice daily

Dabigatran

Tenofovir

For management of other concomitant medications, refer to SmPC, EASL practice guidelines and http://hep-druginteractions.org/

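### The protocol gives two incompatible rules for amiodarone: prohibited in 17.5, but allowed with monitoring or caution in 12.2 and 15.17

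*Protocol*

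**What the plan says.** Three current sections of the protocol deal with amiodarone.

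- **17.5** explains why severe bradycardia and heart block are of special interest (they have been seen when sofosbuvir is combined with drugs that lower heart rate) and adds in brackets "note amiodarone is prohibited".
- **12.2** opens its drug list by saying that "concomitant use of the following medications are contraindicated". After the named drugs come a line on proton-pump inhibitors and then "Amiodarone should be avoided and if necessary, close monitoring is required". A closing sentence reads "Participants taking these medications must have discontinued prior to starting" (sofosbuvir/velpatasvir).
- **15.17** begins with "the following list of concomitant medications are not permitted, according to product SmPCs" and repeats the contraindicated list and the conditional amiodarone line. It then starts a second list, "The following medications should be co-administered with caution", in which amiodarone appears again.

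On washout, the screening history in 13.8.3 states "prohibited concomitant medications must be discontinued at least 21 days before treatment start as per Exclusions section of protocol". Sections 12.2 and 15.17 require only that the drugs be stopped before treatment starts and give no number of days.

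**The concern.** Whether a trial bans a drug or allows it under conditions should have one answer wherever a site looks. Here a reader of 17.5 concludes that amiodarone is banned, and a reader of the caution list in 15.17 concludes that it may be given.

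The question arises at screening and again during treatment, because concomitant drugs are reviewed at later visits. It decides eligibility. It also decides whether a finding must be handled as non-compliance: 22.5 rules out planned deviations and waivers, and requires unintentional deviations to be documented and reported to the chief investigator and sponsor. The hazard is one that the protocol itself names.

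**Working it through.** There is no figure to reproduce, so the check sets the texts side by side.

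**Step 1. What each place says about amiodarone**

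| Place | Status of amiodarone |
|---|---|
| 12.2, amiodarone line | Avoid; usable if needed, under close monitoring |
| 12.2, closing sentence | Listed drugs must have been stopped before treatment; amiodarone not excepted |
| 15.17, amiodarone line | Same as the 12.2 line |
| 15.17, second list | May be given with caution |
| 17.5 | Prohibited |

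Conditional use and use with caution are compatible. Neither is compatible with prohibition. The conflict is therefore between 17.5 on one side and the amiodarone lines of 12.2 and 15.17 on the other, with the closing sentence of 12.2 leaning towards 17.5.

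**Step 2. Does another section settle it?** Section 13.4 sends screeners to the exclusion criteria for the list of prohibited drugs, and that is where the conditional line stands. The protocol also refers sites to the SmPC. That can tell a site how to manage the interaction, but not whether this trial bans the drug, since a sponsor may be stricter than the label. Nothing in the document gives one section precedence.

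**Step 3. When would a site need the answer?** The schedules in 13.8.2 mark a concomitant-drug review at screening and then:

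- Arm A: week 12, which is 1 further review.
- Arm B: weeks 12, 16, 20 and 24, which is 4 further reviews.

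A patient found on amiodarone at screening (weeks 8 to 12) is eligible under the amiodarone line, and ineligible under 17.5 or the closing sentence of 12.2. A participant who starts amiodarone later is within the protocol under the caution list and outside it under 17.5.

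**Step 4. Do the results change?** The primary analysis set (19.5, 19.10) is defined by randomisation and dosing, and the per-protocol set by 90% adherence. Neither depends on concomitant drugs. Under 17.5, special-interest events are reported if serious, whether or not amiodarone was taken.

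**Step 5. Washout.** Let d be the number of days between stopping a listed drug and treatment week 0.

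- 12.2 and 15.17: met when the drug was stopped before week 0, so d ≥ 1.
- 13.8.3: met when d ≥ 21.
- The two differ for d = 1 to 20: such a patient meets 12.2 but not 13.8.3.

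Consent comes at weeks 8 to 12, so d is already fixed when it is checked and cannot be corrected.

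**The case against.** The best defence is that 12.2 and 15.17 are the sections that set drug rules, and they use identical wording. On this reading the contraindicated list is the run of bare drug names ending at modafinil, and the proton-pump-inhibitor and amiodarone lines are separate conditional advice. If the heading and the stopping rule covered those lines, they would also ban proton-pump inhibitors, for which the same text gives timing and a maximum dose. Section 17.5 would then be a stray aside in a section on event reporting. This is a fair account of what was probably meant, but the bracket in 17.5 is still current text that says the opposite, in the paragraph about the very hazard concerned.

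Several stronger inferences are tempting and are not supported:

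- **That 15.17 holds four different rules.** Its opening sentence and its heading introduce the same list, and the conditional line agrees with the caution list.
- **That the lack of a scheduled ECG or heart-rate check is itself a defect.** Monitoring needed only by someone taking amiodarone need not be scheduled for everyone. Section 13.8.3 permits extra visits and further procedures at the investigator's discretion, and sites are referred to the SmPC.
- **That the washout rules contradict each other.** Stopping 21 days ahead satisfies all three sections. What is wrong is the attribution to the exclusion criteria, and that one set of patients passes one section and fails another.
- **That 12.2 points to the wrong place for the caution list** ("Please consult the SmPC and Section 15.16 and 17 for list of medications to be used with caution or monitoring"). This reads readily as shorthand for 15.16 and 15.17.

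**Conclusion.** The inconsistency is real and should be corrected: 17.5 prohibits amiodarone, while 12.2 and 15.17 allow it conditionally, and no other section resolves the difference. It matters for safety, eligibility and deviation handling.

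Its reach is narrow. The protocol gives no frequency of amiodarone use, so the number affected among the 60 planned participants cannot be calculated; I assume it is small. Sections 12.2 and 15.17 also expect the listed drugs to have been stopped under standard care. The sample size, the SVR12 comparison and the reporting of special-interest events are untouched, and a reader should not infer any threat to the efficacy result.

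The washout attribution is minor. It can change eligibility only for a patient who stopped a listed drug 1 to 20 days before week 0.

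**What to change.** State one amiodarone rule in 12.2 and align 15.17 and 17.5 with it. Either option works:

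1. **Prohibit throughout.** Delete the conditional line from 12.2 and 15.17 and the entry in the caution list, and say what happens to study drug if amiodarone becomes necessary during treatment. Cost: a few patients may be excluded; they would complete their NHS 12-week course outside the trial.
2. **Allow monitored use.** Remove the word prohibited from 17.5, set the amiodarone and proton-pump-inhibitor lines apart from the contraindicated list and its stopping rule, and require heart-rate or cardiac monitoring according to the SmPC for any participant taking amiodarone. Cost: extra monitoring for those few participants only.

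In the same amendment, use one washout rule in 12.2, 13.8.3 and 15.17: either add the 21 days to 12.2 and 15.17 or remove it from 13.8.3. Apart from the costs above, the change is to wording only.

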# 17.6 Adverse events that do not require reporting

In clinical trials treatment emergent adverse events associated with sofosbuvir/velpatasvir were reported at similar frequencies to placebo-treated patients. The most frequent events (at  $\geq$ 10%) were headache, fatigue and nausea. Therefore no SAEs are considered 'expected' and SAEs should be reported as detailed in 17.4.

#### 17.7 Notification and Reporting of Serious Adverse Events & SUSARs

All Serious Adverse Event (SAEs) will be recorded in the participants' notes, the CRF, the sponsor SAE form and reported to the sponsor (Joint Research Management Office) within 24 hours of the PI or co-investigators becoming aware of the event. Nominated co-investigators (as listed will be authorised to sign the SAE forms in the absence of the PI at the participating sites. The sponsor will not consider a SAE 'valid' unless there is written evidence of that the SAE has been medically assessed by the PI or delegated qualified medic (see JRMO SOP 26a - Phamacovigilance reporting for CTIMPs).

Suspected Unexpected Serious Adverse Reactions (SUSARs) that occur during the trial will be reported to the JRMO within 24 hours of the PI or co-investigator becoming aware of the event. SUSARs should be reported to the sponsor (JRMO) within 24 hours. The sponsor will report SUSARs fatal or life-threatening SUSARs as soon as possible, but no later than 7 days after you are first aware of the reaction. Any additional relevant information must be sent within 8 days of the report.

You must report non-fatal or non-life-threatening SUSARs as soon as possible but no later than 15 days after you are first aware of the reaction.

# 17.8 Sponsor Medical Assessment

Sponsor has delegated the responsibility for oversight of IMP safety profile and medical assessment of SAEs and SUSARs to the CI. The CI must review all SAEs within 24 hours of receipt. This review should encompass seriousness, relatedness and expectedness. Day 0 for all SUSARs is when the SAE/SUSAR is received by the CI and /or coordinating team and /or sponsor whichever is first.

It is expected that the CI will achieve oversight of IMP safety profile through trial committees as per section 28.0.

It is noted that the CI can upgrade an event to 'related' or 'unexpected' but cannot downgrade the PI assessment of an event to 'unrelated' or 'expected'.

If there is disagreement between CI and PI assessment, it is the CI's responsibility to liaise with the Site PI before CI's final decisions.

The CI and PI assessment can differ.

#### 17.9 Urgent Safety Measures

The CI may take urgent safety measures to ensure the safety and protection of the clinical trial subjects from any immediate hazard to their health and safety, in accordance with Regulation 30. The measures should be taken immediately to protect the safety of trial participants. The MHRA can be informed retrospectively of the measures taken.

The CI has an obligation to inform both the MHRA and Research Ethics Committee in writing within 3 days, in the form of a substantial amendment. The sponsor (JRMO) must be sent a copy of the correspondence with regards to this matter as soon as it is sent.

# 17.10 Procedures for reporting blinded SUSARs

NA

# 17.11 Pregnancy

If a participant or the female partner of a male participant becomes pregnant whilst involved in the study, it should not be considered an SAE or AE but requires reporting, monitoring and follow up. The sponsor should be notified immediately (within 24 hours of site becoming aware of the pregnancy) using the sponsor pregnancy form. The pregnancy reporting procedure will be the same as for SAE.

The CI in conjunction with the site PI will determine if the fetus has been exposed to the IMP. The PI has responsibility to ensure that the pregnancy is form is completed and submitted to the Sponsor within agreed timelines. The initial report should be within 24 hours and follow up information submitted when it becomes available, up to the time of birth.

The PI must follow up the pregnancy until delivery as well as after birth if clinically appropriate. Any events to the mother or child that occur during this time that could be considered an SAE must be reported to the sponsor in line with section 17.7 utilising the sponsor SAE reporting form.

Pregnant female participants should be withdrawn from the treatment, but if willing can be follow up for primary outcome measure. Male participants can continue on the study.

Requirements for contraception during and following the use of the IMPs are documented within their SmPC and therefore do not need to be reported to the manufacturer.

# 18.0 Annual reporting

# **Development Annual Safety Update (DSUR)**

The DSUR will be written by the CI (using Sponsor template) and submitted to the sponsor for review prior to submission to the MHRA. The DSUR is due for submission within 60 days of the end of the reporting period. The reporting period is annually from the date on the "notice of acceptance letter" from the MHRA. As delegated Sponsor Medical Assessor the CI will carry out a risk benefit analysis of the IMPs encompassing all events having arisen on the trial. REC will be sent a copy of the DSUR.

#### **Annual Progress Report (APR)**

The APR will be written by the CI (using HRA template) and submitted to the sponsor for review prior to submission to the REC. The APR is due within 30 days of the anniversary date of the "favourable opinion" letter from the REC.

# 19.0 Statistical and Data Analysis

#### 19.1 Sample size calculation

The planned sample size is 60 participants - with 30 participants in each of two treatment arms. This is based on the assumption of a 30% difference in the primary outcome measure (proportion of patients who achieve SVR12) between the two treatment arms, where SVR in the 12 week treatment arm is 65%, and 95% in the 24 week treatment arm. All outcomes are measured on an intention to treat basis.

Estimates of SVR rates for patients with slow treatment response (week 2 HCV detectable) is derived from post-hoc analyses of cohort studies or clinical trials. For genotype 3 patients with decompensated cirrhosis treated with sofosbuvir and NS5A inhibitor (daclatasvir or ledipasvir) with or without ribavirin, SVR was 65% for patients viraemic at week 2 [14]. There is no data available for this subgroup treated with sofosbuvir/velpatasvir. For all genotype 3 patients with decompensated cirrhosis, SVR was 50% after 12 weeks of sofosbuvir/velpatasvir [16], and 91% for patients with compensated cirrhosis [15]. Another study showed that a combination of 3 negative factors in genotype 3 patients dropped SVR after 12 weeks of sofosbuvir/velpatasvir to 85%, from 95% if only 2 negative factors were present [18].

Given the trial cohort will contain compensated and decompensated patients, the SVR after 12 weeks is estimated at 65%. The study assumes an SVR of 95% with the extended arm, in order for the margin of improvement to be clinically and statistically significant, as well as cost-effective to justify the increased drug costs. This is a realistic assumption given 12 weeks of sofosbuvir/velpatasvir in genotype 3 patients without negative factors (i.e. without cirrhosis) achieved SVR of 97% [15]. This study will demonstrate if treatment extension can overcome the impact of negative treatment factors on SVR.

To detect a true difference between the two treatment arms (if one exists) with 80% power and 95% confidence level, 24 participants are required as a minimum in each arm. The study will recruit 60 participants to allow for withdrawals or those lost to follow up.

Study participants will undergo block randomisation such that at any time during the study, roughly equal numbers will be recruited into both arms, allowing for interim analysis as necessary. An interim analysis may be performed when about 50% of planned recruitment has taken place, to assess safety and efficacy, whether the study sample needs to be altered. This will be determined by the Chief Investigator and/or the Trial Steering Committee.

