#### Predictors of response

Analysis of nearly 500 patients with advanced cirrhosis treated with sofosbuvir + NS5A inhibitor +/-ribavirin within the NHS England Expanded Access Programme found detectable viral load at treatment week 2 to be a significant predictor of treatment failure (OR 2.6, 95% CI 1.1-6.3) [14]. The impact of on-treatment response was strongest for genotype 3 HCV, where there was a 20% difference in failure rate between patients who were viraemic versus non-viraemic by treatment

week 2 (32/10 (30.5%) vs. 7/70 (10.0%) [14]. Amongst 175 genotype 3-infected patients with available HCV result at treatment week 2, 105 (60%) remained viraemic. In this cohort week 2 viral response has a 82% sensitivity and 90% negative predictive value for treatment failure (unpublished data).

Similarly a subanalysis of the clinical trial of genotype 3 HCV infected patients who received sofosbuvir and the NS5A inhibitor daclatasvir showed that for those with cirrhosis, SVR 70% in week 2 viral responders, compared to 50% in patients with detected virus at week 2 [19]. In another study, viral response at week 2 or 4 of treatment with sofosbuvir/velpatasvir did not predict treatment outcome [20] but the analysis used a lower viral threshold than the one used in this protocol. In a further study of genotype 3 infections treated with a number sofosbuvir combination therapies, week 2 viral response again showed predictive value [26].

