# 19.11 Procedure(s) to account for missing or spurious data

To reduce missing data on the primary outcome, SVR12 will be defined as HCV RNA <15iu/mL from 12 to 16 weeks after end of treatment. This widens the window when SVR12 can be reported. A negative HCV RNA at any point after 12 weeks post-treatment is clinically considered to be a sustained virological cure. Negative HCV RNA at less than 12 weeks post-treatment will be considered non-SVR12.

Non SVR12 will be differentiated by true viral relapse or missing data due to lost to follow up, to allow per-protocol analysis.

Given data is time point specific, data outside of the defined window cannot be carried forward to replace missing data.

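### The increase from 24 to 30 per arm does not protect the stated 80% power against missing SVR12, because missing outcomes count as failures, and the 65% control rate needs reconciling with section 9.1

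*Protocol*

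**What the plan says.** Section 19.1 assumes "SVR in the 12 week treatment arm is 65%, and 95% in the 24 week treatment arm" and concludes that, "with 80% power and 95% confidence level, 24 participants are required as a minimum in each arm". It then plans more than this minimum: "The planned sample size is 60 participants - with 30 participants in each of two treatment arms". The reason given is "The study will recruit 60 participants to allow for withdrawals or those lost to follow up". No loss rate is stated. The same section says "All outcomes are measured on an intention to treat basis".

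Section 19.5 includes every randomised participant with at least one dose of study drug, requires arm B participants to have taken at least one extension dose, and compares the arms by chi-square test. Section 19.11 treats missing outcomes as a kind of failure: "Non SVR12 will be differentiated by true viral relapse or missing data due to lost to follow up". It also bars results from outside the window as substitutes.

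For the control rate, section 19.1 cites reference [14] for genotype 3 patients with decompensated cirrhosis: "SVR was 65% for patients viraemic at week 2". Section 9.1 (Predictors of response) cites the same reference for failure rates in viraemic versus non-viraemic genotype 3 patients from a cohort with advanced cirrhosis, printed as "32/10 (30.5%) vs. 7/70 (10.0"%).

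**The concern.** Dividing an evaluable sample size by one minus the loss rate is right when lost patients drop out of the analysis, since it restores the number analysed. It does not work when a lost patient is kept and scored as a failure. The number analysed is then already 30 per arm, but both response rates fall and the difference between them shrinks. Six more patients per arm do not bring that difference back.

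At stake is how a null result would be read. Sections 9.2 and 15.2 say that NHS England would consider adopting the longer course on the strength of this trial. If 19.1 is taken to mean that 80% power survives six losses per arm, a non-significant result could be over-read as evidence that extension does not help. The control rate matters too: a higher true rate in the 12-week arm leaves less room for improvement.

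**Working it through.** **Inputs.** From 19.1: rates 65% and 95%, 80% power, 95% confidence (read as two-sided 5%; sidedness is not stated), 24 and 30 per arm. From 13.5.1: 1:1 allocation. From 19.5: chi-square test (continuity correction not stated; taken as uncorrected).

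**1. Reproduce the plan's 24.** The unpooled-variance formula gives

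n = [0.65×0.35 + 0.95×0.05] × (1.960 + 0.842)² / 0.30² = 0.275 × 7.849 / 0.09 = 23.98, so 24.

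Exact power of the uncorrected chi-square test at 24 per arm is 80.8%. The figure therefore stands for patients with an outcome. (The pooled-variance formula gives 27.)

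**2. What 24 to 30 would imply.** (30 − 24)/30 = 20%, and 24/(1 − 0.20) = 30. The 20% is inferred from these two numbers; the protocol does not state it.

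**3. Power when missing counts as failure.** Suppose 65% and 95% are rates among patients with an outcome, and a fraction d is missing in each arm. The analysed rates are 0.65(1 − d) and 0.95(1 − d), and the difference is 0.30(1 − d). At 30 per arm:

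| Missing, d | Analysed rates | Difference (points) | Exact power | Normal approximation |
|---|---|---|---|---|
| 0% | 65.0% vs 95.0% | 30.0 | 88.0% | 84.6% |
| 3% | 63.1% vs 92.2% | 29.1 | 80.8% | 78.6% |
| 5% | 61.8% vs 90.3% | 28.5 | 76.3% | 74.6% |
| 10% | 58.5% vs 85.5% | 27.0 | 66.1% | 65.1% |
| 20% | 52.0% vs 76.0% | 24.0 | 48.9% | 49.0% |

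The exact figure crosses 80% at about 3.3% missing. Since 0.033 × 30 = 1, the extra patients absorb about one missing outcome per arm, against the six that 24 to 30 suggests.

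**4. The other reading.** If 65% and 95% already count losses as failures, no further dilution applies. Power at 30 per arm is the first row: 88.0% exact, 84.6% by approximation.

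**5. The control rate.** Section 9.1 says that 105 of 175 patients were viraemic at week 2. 32/105 = 30.5%, which matches the printed percentage; so do the stated sensitivity, 32/(32 + 7) = 82%, and negative predictive value, (70 − 7)/70 = 90%. The denominator is therefore 105. If failure is the complement of SVR, SVR is 1 − 32/105 = 69.5%, which is 4.5 points above 65%. With 69.5% versus 95% and nothing missing, power at 30 per arm is 79.0% exact (74.6% by approximation).

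**The case against.** Several things count against a harsher conclusion.

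- **Expected loss is low.** A reader might infer that the trial has only even odds of detecting its planned effect. The documents do not support that. The 49% needs 20% of outcomes missing in both arms, whereas 19.2 expects few withdrawals and enrols patients at weeks 8–12 with at least 90% adherence.
- **The rates may already be intention-to-treat.** The intention-to-treat sentence directly follows the 65% and 95% in 19.1. On that reading, step 3 counts losses twice. This stands as a live alternative.
- **Not every withdrawal is a failure.** Section 19.11 speaks of missing data from loss to follow-up. Sections 13.8.4, 13.9 and 13.10 allow SVR12 to be collected after withdrawal with consent, and patients who stop treatment may stay in follow-up. Arm B patients with no extension dose leave the analysis set under 19.5, and for them extra recruitment is a valid allowance.
- **There are safeguards.** Section 13.9 allows replacement of withdrawn patients if the sample is judged underpowered, 19.9 allows an interim look at sample size, and 19.10 allows a per-protocol analysis if loss is high. These bear on the consequence, but none removes the dilution in the primary analysis.
- **65% may be a judgement.** A reader might call it a proven error against 69.5%. The two sections describe the populations differently, the source is not available here, and 19.1 presents 65% as an estimate for a mixed cohort, beside other cited rates of 50%, 85% and 91%. It is an unexplained discrepancy. Combining 69.5% with 20% loss would give 38% power, but that stacks an inferred rate on a loss that nobody has predicted.

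**Conclusion.** The sentence giving the reason for recruiting 60 is wrong as written for patients lost after dosing: they remain in the primary analysis as non-SVR12, so the extra six per arm do not offset them. This holds whichever way the assumed rates are read.

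The size depends on that reading. If 65% and 95% apply to patients with an outcome, 80% power survives only about 3% missing. If they are already intention-to-treat rates, power is about 85–88% and the fault is confined to the stated rationale. The protocol does not say which. These figures assume equal loss in both arms, a two-sided 5% level and an uncorrected chi-square test. With a continuity correction, exact power with nothing missing is 78.8%.

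The 65% and the 30.5% failure rate need reconciling because the choice takes power with no loss from 88% to 79%.

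**What to change.** Keep 60 patients and revise section 19.1 as follows.

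1. State whether 65% and 95% include losses counted as non-SVR12.
2. Replace the single power statement with power at 30 per arm by rate of missing SVR12. For example, if the rates exclude losses: 88% at none, about 80% at 3%, 76% at 5% and 66% at 10%. State the test and whether it is continuity-corrected.
3. Limit the withdrawal rationale to patients who leave the analysis set, namely arm B patients with no extension dose.
4. Explain how 65% relates to the 30.5% failure rate cited in 9.1 from the same reference, correct the printed denominator there, and show power at both control rates.
5. Say that routine SVR12 results, for which consent is already sought (13.8.4, 13.9), will be actively retrieved within the 12-to-16-week window so that few primary outcomes are missing.

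The cost is rewording, some follow-up effort, and a less favourable stated power. No patients are added, and the endpoint and test do not change.
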